## ABBREVIATIONS

Term	Definition
AACR	American Association for Cancer Research
ACE2	Angiotensin Converting Enzyme 2
ACVPU	Alert, Consciousness, Verbal, Pain, Unresponsive Scale
AE	Adverse Event
ALT	Alanine Transaminase
ANC	Absolute Neutrophil Count
APTT	Activated Partial Thromboplastin Time
AR	Androgen Receptor
ARDS	Acute Respiratory Distress Syndrome
AST	Aspartate Transaminase
ATC	Anatomical Therapeutic Chemical
AUC	Area under the Curve
BID	Twice a Day
BP	Blood Pressure
BMI	Body Mass Index
CDC	Centers for Disease Control and Prevention
CFR	Code of Federal Regulations
CHO	Chinese Hamster Ovary
CI	Confidence Interval
CIOMS	Council for International Organizations of Medical Sciences
CK	Creatinine kinase
CLIA	Clinical Laboratory Improvement Amendments
CMH	Cochran–Mantel–Haenszel
CMP	Clinical Monitoring Plan
CMS	Clinical Material Services
CNS	Central Nervous System
Cr	Creatinine
CR	Complete Response
CRF	Case Report Form
CRO	Contract Research Organization
CROMS	Clinical Research Operations and Management Support
CRP	C-reactive Protein
CRPC	Castrate Resistant Prostate Cancer
COVID-19	Coronavirus Disease 2019
CQMP	Clinical Quality Management Plan
CSR	Clinical Study Report
CTCAE	Common Terminology Criteria for Adverse Events
DAIDS	Division of Allergy and Infectious Diseases
DCR	Disease Control Rate

DHHS	Department of Health and Human Services
DMC	Data Monitoring Committee
DMID	Division of Microbiology and Infectious Diseases
DLT	Dose Limiting Toxicity
DMP	Data Management Plan
EC	Ethics Committee
ECOM	Extracorporeal Membrane Oxygenation
EOS	End of Study
EUA	Emergency Use Authorization
FDA	Food and Drug Administration
FiO2	Fraction of Inspired Oxygen in the Air
FWA	Federal Wide Assurance
GCP	Good Clinical Practice
GLP	Good Laboratory Practices
hEGR	Human Ether-a-go-go-related Gene
Hgb	Hemoglobin
HR	Heart Rate
IB	Investigator's Brochure
IC50	A quantitative measure that indicates how much of a particular inhibitory substance (e.g., drug) is needed to inhibit, in vitro, a given biological process or biological component by 50%
ICD	International Classification of Diseases
ICF	Informed Consent Form
ICH	International Council for Harmonization
ICU	Intensive Care Unit
IIT	Institute Initiated Trial
IND	Investigational New Drug Application
INR	International Normalized Ratio
iNOS	Inducible Nitric Oxide Synthase
IRB	Institutional Review Board
IV	Intravenous
IWRS	Interactive Web Response System
IxRS	Interactive Web/Voice Response System
LLOQ	Lower Limit of Quantitation
LNCaP	Lymph Node Carcinoma of the Prostate
MCG	Microgram
MedDRA	Medical Dictionary for Regulatory Activities
MERS	Middle East Respiratory Syndrome
MG	Milligram
MOP	Manual of Procedures
MTD	Maximum Tolerated Dose
N	Number (typically refers to subjects)

NDA	New Drug Application
NIAID	National Institute of Allergy and Infectious Diseases
NIH	National Institutes of Health
NP	Nasopharyngeal
NOAEL	No Observed Adverse Effect Level
NSAID	nonsteroidal anti-inflammatory drug
OHRP	Office for Human Research Protections
OP	Oropharyngeal
OTC	Over-the Counter
PCR	Polymerase Chain Reaction
PD	Protocol Deviation
PHI	Protected Health Information
PI	Principal Investigator
PLT	Platelet
PP	Per Protocol
PR	Partial Response
PSA	Prostate-Specific Antigen
PT	Prothrombin Time
QD	Once A Day
QT Interval	Measured from the Beginning of the QRS Complex to the End of the T wave
QTc	Corrected Q-T Interval
RNA	Ribonucleic Acid
RBC	Red Blood Cell
RECIST	Response Evaluation Criteria in Solid Tumors
RT-PCR	Reverse Transcription-Polymerase Chain Reaction
SAE	Serious Adverse Event
SAP	Statistical Analysis Plan
SARS	Severe Acute Respiratory Syndrome
SARS-CoV-2	Severe Acute Respiratory Syndrome Coronavirus 2
SC	Steering Committee
SD	Stable Disease
SDCC	Statistical and Data Coordinating Center
SDSP	Study Data Standardization Plan
SMC	Safety Monitoring Committee
SNP	Single Nucleotide Polymorphisms
SOA	Schedule of Activities
SOC	System Organ Class
SOP	Standard Operating Procedure
SpO2	Saturation of Peripheral Oxygen
SUSAR	Suspected Unexpected Serious Adverse Reaction
T.Bili	Total Bilirubin

---

TEAE	Treatment Emergent Adverse Events
TMPRSS2	Transmembrane Protease Serine 2
TNF	Tumor Necrosis Factor
ULN	Upper Limited Number
UP	Unanticipated Problem
US	United States
WBC	White Blood Cell
WHO	World Health Organization

Sponsor Signature Page	.....	- 2 -
Investigator Statement	.....	- 3 -
Abbreviations	.....	- 4 -
Protocol Summary	.....	1
Synopsis .....	.....	1
Schedule of Activities (SoA) .....	.....	11
Amendment 1(11-JUN-2021)	.....	
1 .....	.....	BACKGROUND
	.....	15
Overview of Disease Pathogenesis, Epidemiology, and Current Treatment .....	.....	15
Epidemiology.....	.....	15
Pathogenesis .....	.....	15
Available Therapeutic Options in COVID-19 .....	.....	15
Role of Androgen Receptor Antagonist in COVID-19 .....	.....	15
Introduction to Investigational Treatment(s).....	.....	16

## PROTOCOL SUMMARY

### Synopsis

#### Protocol Title:

A Randomized, Double-blind, Placebo-Controlled, Phase 3 Study to Evaluate the Efficacy and Safety of Proxalutamide (GT0918) in Outpatients with Mild to Moderate COVID-19 Illness.

**Short Title:** A Phase 3 Study to Evaluate the Efficacy and Safety of GT0918 in Outpatients with Mild to Moderate COVID-19 Illness

**Protocol Number:** GT0918-US-3001

**Study Phase:** 3

**Sponsor:** Suzhou Kintor Pharmaceuticals, Inc.

#### Rationale:

Coronavirus disease 2019 (COVID-19) emerged in late 2019 and spread rapidly, resulting in a global pandemic. New COVID-19 cases and deaths have been constantly rising. COVID-19 is caused by a novel coronavirus (SARS-CoV-2), and infected persons can have a wide range of disease severity, with many patients showing mild or moderate disease. Although many therapies have been and are being explored in various stages of COVID-19, for the large population with mild and moderate COVID-19, limited treatments are available. There is a huge unmet medical need for home-use, oral intake, treatments for mild to moderate COVID-19 patients to ameliorate symptoms and prevent hospitalization.

Much research has proven that SARS-CoV-2 cell entry and fusion depends on angiotensin converting enzyme 2 (ACE2) and transmembrane protease serine 2 (TMPRSS2). In humans, androgens are the only known transcription promoters for the TMPRSS2 gene. Further, the ACE2 receptor, also critical for SARS-CoV-2 viral infectivity, is affected by male sex hormones with higher activity found in males. So, androgen receptor antagonists have the potential to reduce virus entry and viral infectivity.

Proxalutamide (GT0918), a new investigational androgen receptor (AR) antagonist with more specificity and activity in inhibiting androgen receptors, has shown to inhibit the expression of ACE2 and TMPRSS2 in lung epithelial cells. GT0918 can also down-regulate the protein expression level of inflammation-related factor inducible nitric oxide synthase (iNOS) and the mRNA expression level of iNOS and tumor necrosis factor (TNF). Recent research showed that GT0918 inhibited SARS-CoV-2 infection more effectively than Enzalutamide in LNCaP cells in a dose-dependent manner, with concentration that inhibits response by 50% (IC50) values of

97 nM. Furthermore, the preclinical results suggest that GT0918 should more effectively inhibit AR-dependent expression of ACE-2 and TMPRSS2 than Enzalutamide in a variety of SARS-CoV2 infected organs, including lung, Gastrointestinal (GI), heart, and kidney.

The clinical study of GT0918 treatment in Brazil for COVID-19 outpatients (NCT04446429) showed the hospitalization rate was significantly decreased in the GT0918 group compared with placebo group (0 vs. 27% in the male cohort and 3 vs. 19% in the female cohort). No serious adverse event (SAE) occurred in the GT0918 group compared with 27% in the placebo group in the male cohort. In the female cohort, the percentage of subjects reported to have SAEs was 3% in the GT0918 group and 19% in the placebo group.

GT0918 will be administered to evaluate its effect in accelerating recovery following SARS-CoV-2 infection, limiting spread into lung cells, improving the clinical outcome and reducing hospitalization in COVID-19 infected outpatients with mild or moderate symptoms.

### **Objectives and Endpoints:**

Objectives	Endpoints
Primary	Primary
To evaluate the efficacy in terms of clinical status following treatment with GT0918 compared to placebo	Percentage of subjects who do not experience any of the following events due to all causes by Day 28: 

• Hospitalization for <math>\geq</math> 24 hours or

• Supplemental oxygen for <math>\geq</math> 24 hours in response to SpO2 <math>\leq</math> 93% or

• Death

Secondary	Secondary
	•

To evaluate the clinical efficacy of GT0918 compared to placebo using the NIAID 8- point scoring scale	
Percentage of subjects achieving each clinical status by Days 7, 14 and 28 as defined below based on The National Institute of Allergy and Infectious Diseases (NIAID) 8- point scoring scale:
 
 
1 Death
 
2 Hospitalized, on invasive mechanical ventilation or extracorporeal membrane oxygenation (ECMO)
 
3 Hospitalized, on non-invasive ventilation or high flow oxygen devices
 
4 Hospitalized, requiring supplemental oxygen
 
5 Hospitalized, not requiring supplemental oxygen - requiring ongoing medical care (COVID-19-related or otherwise)
 
6 Hospitalized, not requiring supplemental oxygen - no longer requires ongoing medical care
 
7 Not hospitalized, limitation on activities and/or requiring home oxygen
 
8 Not hospitalized, no limitations on activities
 

To evaluate the clinical efficacy of GT0918 compared to placebo based on clinical status	
 
• Proportion of subjects with all-cause hospitalization (defined as <math>\geq 24</math> hours) by Day 28
 
• Proportion of subjects hospitalized (defined as <math>\geq 24</math> hours) due to COVID-19 related events by Day 28
 
• Days of hospitalization due to all causes or COVID-19
 
• Proportion of subjects with all-cause mortality by Day 28
 
• Proportion of subjects with COVID-19 related mortality by Day 28
 
• Proportion of subjects admitted to an ICU due to COVID-19 by Day 28
 
• Days in intensive care unit (ICU)
 
• Proportion of subjects requiring supplemental oxygen, high-flow oxygen, any ventilation or ECMO due to COVID-19 by Day 28
 
• Proportion of subjects requiring mechanical ventilation or ECMO due to COVID-19 by Day 28
 
• Days on supplemental oxygen/high flow oxygen devices/mechanical ventilation
 
• 
 

Characterize the effect of GT0918 compared to placebo on symptom improvement or resolution	
Symptom Improvement:
 
 
• Change in symptom score (total of ratings) from baseline to Days 3, 7, 14 and 28
 
• Time to symptom improvement
 
• Proportion of subjects demonstrating symptom improvement via the symptom questionnaire (total of ratings) on Days 3, 7, 14 and 28
 
 
Symptom resolution:

	
 
• Proportion of subjects demonstrating symptom resolution via the symptom questionnaire on Days 3, 7, 14 and 28
 
• Time to symptom resolution
 

Characterize the effect of GT0918 compared to placebo on SARS-CoV-2 viral load clearance	
 
• Change from baseline to Days 3, 7, 14 and 28 in SARS-CoV-2 viral load
 
• Proportion of subjects that achieve SARS-CoV-2 clearance (Days 3, 7, 14 and 28)
 
• Time to SARS-CoV-2 clearance
 
• SARS-CoV-2 viral load area under the concentration-time curve (AUC) assessed to days 3, 7, 14 and 28
 

Characterize the effect of GT0918 compared to placebo on safety	Safety assessments such as AEs, SAEs and laboratory data
Exploratory	Exploratory
Characterize the pharmacokinetics of GT0918	
 
• Mean trough concentration of GT0918 and GT0955 on Days 1, 3, 7 and 14
 
• To explore relationships between GT0918 and/or GT0955 exposure and selected efficacy and safety endpoints and/or biomarkers
 

Characterize emergence of viral resistance to GT0918	
Screening for novel mutants in subjects who do not respond to GT0918
 
 
• Genotype of SARS-CoV-2 viral isolates
 

To explore biomarkers predictive of GT0918 safety, efficacy, and/or disease progression and COVID-19 clinical outcomes	
 
• The association between changes in disease related biomarkers with clinical endpoints
 

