### **10.5.2.9 Viral load reduction**

SARS-CoV-2 viral load, including changes from baseline, will be summarized and plotted by treatment and listed. Baseline is defined as the Day 1 pre-dose assessment. Changes from baseline to Day 3, 7, 14 and 28 in SARS-CoV-2 viral load data in the log base 10 scale will be analyzed using a linear mixed-effect model.

The AUC from Day 1 pre-dose to Day 28 (AUC[0-D28]) will be calculated according to the linear trapezoidal rule using the measured SARS-CoV-2 viral load-time values above the lower limit of quantification. No imputations of missing data will be conducted. No AUC(0-D28) values will be calculated when Day 1 pre-dose and/or Day 28 values are missing, or if there are more than 3 values missing in the profile.

The AUC (0-D28) will be summarized and plotted by treatment and listed.

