If a patient has not experienced SARS-CoV-2 clearance by completion or early discontinuation of study/study treatment, the patient will be censored at the date of their last visit during the post-treatment period.

Time to SARS-CoV-2 clearance will be applying the same KM methods and Cox proportional hazard models introduced for the time to sustained 100% SARS CoV-2 viral reduction analysis.

Viral Load AUC

SARS-CoV-2 viral load area under the concentration-time curve (AUC) will be calculated according to the linear trapezoidal rule using the measured SARS-CoV-2 viral load-time values above the lower limit of quantification (LoQ) at Days 3, 7, 14 and 28. Per ICON central lab, LoQ is 59.9 copies/mL. No imputations of missing data will be conducted. No AUC(0-D28) values will be calculated when Day 1 pre-dose and/or Day 28 values are missing, or if there are more than 3 values missing in the profile. The AUC (0-D28) will be summarized and plotted by treatment group and listed.

Viral Resistance by Day 28

The proportion of viral resistance at day 28 will be summarized by treatment group and listed. The CMH chi-square test introduced for the primary endpoint analysis will be used to compare the difference of proportion of viral resistance between treatment groups by day 28.

Viral resistance is defined as when subjects:

- Are not able to show two consecutive negative test results via ddPCR testing by Day 28 without any missing scheduled tests, and/or

- Show a positive real-time ddPCR test result after two consecutive negative ddPCR test results, and/or
- A confirmed rise in SARS-CoV-2 RNA of ≥ 1 log10 after achieving nadir on treatment.

COVID-19 Ordinal Outcomes Scale

Below summaries will be provided using mITT set:

- The percentage of subjects at each clinical status using NIAID 8-point ordinal scale at Days 3, 7, 14, and 28

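### Viral-load AUC is listed to Days 3, 7, 14 and 28, but the only planned output is a descriptive AUC(0-D28), with no estimated treatment difference and with subjects lacking a Day 28 value left out

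*Protocol*

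**What the plan says.** **Endpoint lists.** The protocol synopsis, protocol sections 3 and 7.2.7, and SAP 3.3.2 all carry the same item: "SARS-CoV-2 viral load area under the concentration-time curve (AUC) assessed to days 3, 7, 14 and 28". In the synopsis it sits under the objective "Characterize the effect of GT0918 compared to placebo on SARS-CoV-2 viral load clearance".

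**Protocol 10.5.2.9.** One AUC is defined: "The AUC from Day 1 pre-dose to Day 28 (AUC[0-D28]) will be calculated according to the linear trapezoidal rule". One output follows: "The AUC (0-D28) will be summarized and plotted by treatment and listed".

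**SAP 4.10.3, Viral Load AUC.** The trapezoidal rule is applied to values "above the lower limit of quantification (LoQ) at Days 3, 7, 14 and 28", with the LoQ given as 59.9 copies/mL. On missing data the SAP states "No imputations of missing data will be conducted" and "No AUC(0-D28) values will be calculated when Day 1 pre-dose and/or Day 28 values are missing", and it also voids the AUC when more than three values in the profile are missing. The only output named is: "The AUC (0-D28) will be summarized and plotted by treatment group and listed".

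**Revision history.** The SAP's revision history itemises removed analyses, such as ICU, mortality and ventilation endpoints. AUC to Days 3, 7 and 14 is not among them. Protocol 10.1 lets the SAP prevail where the two documents differ, but the SAP's own endpoint list still holds all four horizons.

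**The concern.** The endpoint list promises four quantities and the analysis section delivers one. The shorter horizons are the ones that lie within dosing, which ends at Day 14 (protocol 6.1.5). Half of the 28-day window is off treatment.

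Two things are at stake. First, a subject with baseline, Day 3, Day 7 and Day 14 swabs holds complete data for three listed endpoints, yet appears in no named AUC output if the Day 28 swab was missed. Second, the endpoint serves a comparison with placebo, but no AUC has an estimate of that comparison. Leaving the list and the analysis in disagreement also allows the horizon to be chosen after the data are seen.

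**Working it through.** The documents state no power, effect size or sample size for AUC, so there is no planned figure to reproduce. The check compares passages and then counts.

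**1. Listed against planned**

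| AUC horizon | Listed in SAP 3.3.2 | Named output in SAP 4.10.3 | Treatment difference or CI |
|---|---|---|---|
| Day 3 | yes | none | none |
| Day 7 | yes | none | none |
| Day 14 | yes | none | none |
| Day 28 | yes | by-arm description | none |

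Four are listed, one is reported and none has an inferential comparison. Unreported: 4 − 1 = 3.

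**2. The other virologic endpoints in SAP 3.3.2**

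- Change in viral load: t-tests, Day 3 ANCOVA, MMRM.
- Sustained 100% reduction, and clearance: GEE for each.
- Time to each of these: log-rank test and Cox model.
- AUC: nothing.

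AUC is the only one of the six without a test or model.

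**3. Which missing-data rule excludes subjects**

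The Schedule of Activities gives five planned swabs (baseline, Days 3, 7, 14 and 28), apart from the early-withdrawal swab. AUC(0-D28) needs baseline and Day 28. With both present, at most 5 − 2 = 3 values can be missing, so the rule voiding profiles with more than three missing never applies. The end-point requirement does all the excluding. It also follows that AUC(0-D28) may be a single straight line from baseline to Day 28 with every intermediate swab absent.

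**4. Illustration of the loss**

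Assumptions, none from the documents except N: 668 subjects, all with a baseline, and each later swab missing independently with probability m.

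- No AUC(0-D28): 668 × m.
- Of these, with a Day 14 swab: 668 × m × (1 − m).

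| m | No AUC(0-D28) | Of these, Day 14 swab present |
|---|---|---|
| 5% | 33 | 32 |
| 10% | 67 | 60 |
| 20% | 134 | 107 |
| 30% | 200 | 140 |

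Independence is a simplification. If subjects who miss Day 28 have mostly left by Day 14, the last column is smaller.

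**5. Values below the LoQ**

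The trapezoid uses only values above 59.9 copies/mL. Neither document says whether a below-LoQ Day 28 result counts as missing, or what value it takes if it does not. If it counts as missing, subjects whose virus has fallen below the LoQ drop out of AUC(0-D28). Any rule requiring an end-day value therefore needs a below-LoQ rule beside it. The scale of the AUC, raw or log10, is also unstated.

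**The case against.** Four points can be made for the plan.

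- **The shorter AUCs may be calculated.** The SAP phrase "above the lower limit of quantification (LoQ) at Days 3, 7, 14 and 28" can refer to AUC horizons or to sampling days, and the Day 28 rule is written for AUC(0-D28) only. This stands. A reader might infer that the shorter AUCs are never computed, but the text does not settle that. It shows only that no output is named for them.
- **The virologic question is answered elsewhere.** A reader might infer that subjects without a Day 28 swab contribute nothing, or that the objective cannot be addressed. The documents do not support either reading. Such subjects still enter the Day 3, 7 and 14 t-tests where swabbed, the MMRM and the clearance analyses, all of which compare arms. The gap is confined to the AUC endpoint.
- **A descriptive summary of one secondary endpoint is permissible.** Protocol 10.5.2.9 planned AUC that way while giving viral-load change a mixed model. Wanting an estimate with an interval is partly a matter of judgement. The mismatch between listed and reported horizons is not.
- **More comparisons have a price.** SAP 4.10.1.2 adjusts only for the interim look, so further secondary tests are uncontrolled. This stands and is reflected in the fix.

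It is also tempting to argue that early AUC would detect an effect better than AUC(0-D28). Nothing in the documents shows this. Protocol 2.1 expects more benefit from early use of the drug, which concerns when treatment starts, not which AUC horizon is most sensitive.

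**Conclusion.** The point holds in limited form. Three of the four listed AUC horizons have no planned output, none of the four has an estimated treatment difference or CI, and a subject missing only the Day 28 swab is left out of the AUC summary. These counts rest on the text alone.

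How many subjects are affected is unknown. The table in the working rests on assumed missing rates. SAP 4.10.1.1.3 describes missing primary assessments as relatively frequent, which makes loss by Day 28 plausible, but that statement concerns the primary endpoint and not swabs.

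The primary endpoint, its error control and the sample size are untouched. This is a secondary-endpoint correction worth making because the data are already collected and a suitable model is already in the SAP.

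**What to change.** In SAP 4.10.3, Viral Load AUC:

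1. Define AUC(0-D3), AUC(0-D7), AUC(0-D14) and AUC(0-D28) as trapezoidal areas under log10 viral load, meaning the area of the log10 values and not the log of a raw area.
2. For each, require a measured baseline and a measured value at its own end day, and state how many intermediate swabs may be missing. This replaces the rule on more than three missing values, which never applies.
3. Count a below-LoQ result as observed, at one fixed value stated in advance, and not as missing.
4. Report each AUC by arm with a treatment difference and 95% CI from the ANCOVA already specified for Day 3 viral load (treatment, age, stratification factors, baseline viral load).
5. Label these results supportive, with no multiplicity control.

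The cost is SAP wording, a few extra outputs from existing swabs, and four more correlated, unadjusted secondary comparisons. If the sponsor does not want the shorter horizons, the lesser remedy is to remove them from the endpoint lists with a stated reason. That makes the documents agree but gives up the early data.

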## Study Design

### Overall Design:

This is a Phase 3, randomized, double-blind, placebo-controlled, multicenter study to evaluate the safety and efficacy of Proxalutamide (GT0918) in adult outpatients diagnosed with mild to moderate COVID-19.

The population of subjects with mild to moderate COVID-19 illness will be chosen to evaluate if anti-androgen therapy may effectively prevent progression to the severe form of COVID-19 illness by treating this population early in their disease course and prior to respiratory compromise and failure.

This study utilizes an adaptive design that maximizes efficiency in identifying a safe and efficacious therapeutic agent for COVID-19 during the current outbreak. The study is a multicenter trial that will be conducted in the United States (US) and other countries. Approximately 668 subjects will be randomized in a 1:1 ratio to either GT0918 or placebo. There will be one interim analysis. The interim analysis will be conducted when 334 subjects complete Day 28 after first dose. The blood samples for

---

population (pop) PK analysis need to be collected for at least 100 subjects, whom will also be randomized into the interventional treatment or placebo group with 1:1 ratio.

